**Fig. 7. Study Phases: Baseline & Randomization** includes 2 Sound Sweeps tests: Test 1 with PBO and  $\approx$  5-7 days later Test 2 with either AMPH or PBO. **Treatment Phase** includes 30 TCT sessions with outcome measures after 10, 20 and 30 sessions. **Post-treatment** tests assess both immediate biomarker changes and 12-week durability of outcome gains.

**Assessments:** 30 sessions of TCT will be completed, based on our findings (Fig. 4) and evidence that TCT efficacy is dose-dependent. Assessment dates could be based on either: 1. session # (10, 20 and 30 and 12 weeks later); or 2. Time (days) since starting TCT. In our experience TCT rates closely match 3/week (30 sessions mean = 65 days; 90% of subjects completed their 30 TCT sessions within 11 weeks. Primary analyses will be based on session #, but session dates are recorded and confirmatory analyses will define assessment points based on time passage. Candidate predictive biomarkers are re-tested after session 30.

**General Clinical Monitoring:** In addition to their established ongoing care, patients are carefully monitored at each session as per our well-established procedures, and through to the week-22 follow-up, for any clinical changes. Each week, a member of our research staff checks vital signs and weight, does a detailed assessment of symptom changes, focusing on psychosis, depression, suicidality and abnormal movements, and tests UTox and pregnancy. A designated unblinded staff member processes UTox results in the event that a PBO-arm subject tests positive for amphetamine; any clinical worsening or UTox positive for recreational drugs (other than AMPH in AMPH-arm subjects) or a positive pregnancy test is promptly reviewed with the on-site Psychiatrist; any “yes” on the Columbia Suicide Severity Rating Scale (C-SSRS) “Since Last Visit”, or an exacerbation of psychotic symptoms, prompts detailed review, with appropriate clinical interventions. Patients testing positive for recreational drugs will be retested in 1 week; patients with 3 positive tests no longer continue in the study. **Data from subjects who, for this or other reasons, do not complete the full study are carried forward in an “intent to treat” design, and their data are analyzed using linear mixed models.**

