A “Go” decision requires: 1) confirmation of target engagement (APS learning, AMPH>PBO,  $p < 0.05$ ); 2) evidence of gains from PACT ( $d \geq 0.5$  (AMPH > PBO)) in primary clinical, neurocognitive and/or functional measures (Fig. 8), and 3) the absence of adverse effects of AMPH that are significantly greater than PBO levels. The decision to not use traditional statistical significance as “Go” criteria for Aim 2 reflects this RFA’s call for “Pilot” studies, the need to identify candidate treatments for a subsequent larger “n” Confirmatory Efficacy R01 study, and the limits in sample size resulting from the 3-year R33 duration. Cohen defined a medium effect size ( $d=0.5$ ) as one that is “visible to the naked eye,” and this amount of change is viewed as clinically meaningful in trials targeting negative symptoms. This  $d=0.5$  “Go” threshold for Aim 2 corresponds to a “number needed to treat” (NNT) value  $\approx 3.62$ . While a “Go” decision does not require identification of a biomarker predicting greater PACT

sensitivity (Aim 3), the identification of one or more meaningful predictors that could be incorporated into a Confirmatory Efficacy trial would favorably impact a “Go” decision.

Staff assessing outcome measures are blind to treatment arm, and for some measures receive training using videotaped and practice interviews until achieving high (ICC>.80) reliability based on 20 assessments by 2 raters. We achieve high inter-rater reliability (e.g., ICC>0.85 for PANSS total), and check for rater drift each 90d.

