### 4.3. Outcome Measures

Type	Name	Time Frame	Brief Description
Primary	Auditory Processing Speed (APS) learning	Test 1 and Test 2, one week apart	APS is measured before and after the TCT "Sound Sweeps" frequency modulation session, to determine the amount of "learning", based on the reduction in detection gap (ms). More learning (greater gain in processing speed) with amphetamine vs. placebo confirms target engagement, which is the primary outcome of Aim 1.
Primary	PANSS: Positive & Negative Symptom Scale total	baseline vs. post-TCT session 10, 20 and 30 (approximately 10 weeks), and 12 weeks post-TCT	TCT reduces both positive and negative symptoms of psychosis; we predict that amphetamine will augment these effects via enhanced TCT learning, detected by the PANSS. For this reason, and based on the need to limit total outcome measures, PANSS Total Score is the primary clinical outcome measure. Positive and negative symptom subscales, as well as PANSS factor-derived measures, will be assessed in exploratory analyses. Other secondary clinical measures will include: 1) Psychotic Symptom Rating Scales (assesses auditory hallucinations); 2) Young Mania Rating Scale; 3) Patient Health Questionnaire-9 (current depressive symptoms); 4) Abnormal Involuntary Movement Scale; 5) Columbia Suicide Severity Rating (C-SSRS); "Lifetime/Recent version" at screen; "Since Last Visit" at follow-up visits). The C-SSRS is a sensitive measure of suicidal ideation; any "yes" in C-SSRS prompts an immediate full evaluation/action plan by a study M.D.; and 7) AMPH Cessation Symptom Assessment

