General Statistical Approach: Hypothesis tests are 2-sided ($\alpha=.05$). Type I error is controlled by selecting optimal *a priori* targets for primary analyses; secondary analyses use false discovery rate corrections. When appropriate, missing data are handled via multiple imputation or full information maximum likelihood estimation. Expected drop-out rates and ways to minimize them are described in the parent application.

Differential drop-out rates from PBO vs. AMPH arms are monitored. Clinical follow-up is pursued with all patients exiting the study through post-TCT week 12.

Cohort differences: For between-subject contrasts (drug), baseline demographic, clinical, antipsychotic/anticholinergic load and performance differences are tested and used as covariates if indicated. Sex differences are tested for all measures.

Procedures for Alternative or Unexpected Results: Linear mixed-effects models allow for the analysis of all available data using an intent-to-treat approach. This approach, however, assumes that data are missing at random. A potential concern is nonrandom dropout, particularly when dropout is related to the (missing) outcomes; that is, not missing at random. To make the missing at random assumption more plausible, we will explore the use of auxiliary variables. Auxiliary variables are covariates that predict both dropout and outcomes. By adding auxiliary variables to our models, nonrandom dropout is corrected by conditioning treatment effects on the predictors of dropout.

Primary Efficacy Endpoint(s): Aim 1: Target engagement – APS learning will be significantly greater under AMPH vs. PBO conditions. Aim 2: Pilot trial - Compared to PBO arm patients, AMPH arm patients will exhibit greater clinical benefit, as indicated by one or more of the following: greater, faster or more durable improvements in PANSSt (reduced scores; see below, “Go/No-Go”), MCCBc (increased scores) or WHODAS (reduced scores).

Secondary Efficacy Endpoint(s): Aim 3: Biomarkers - baseline levels of specific neurocognitive or EEG-based measures, or changes in specific measures with initial AMPH exposure, predict greater sensitivity to AMPH-enhanced neurocognitive, clinical or functional gains over 30 sessions of TCT.

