Comparable analytic approaches will be used for neurocognition (MCCBc) and function (WHODAS) as described in "Research Strategy". Data will be described as means with SEM. Tests for normalcy will be applied to all data and non-parametric comparisons will be used if normalcy is not demonstrated. The Analysis Set for these data will be all subjects who have completed 30h of TCT and post-TCT clinical, neurocognitive and function assessments. When appropriate, missing data are handled via multiple imputation or full information maximum likelihood estimation.

Secondary regression analyses assess the predictive value of putative biomarkers on clinical, neurocognitive or functional gains from the addition of AMPH to TCT. Future studies with larger samples will assess potentially more informative models, e.g. Path Analysis to study moderating effects of APS AMPH sensitivity and biomarkers on both indirect (moderated-mediation) and direct paths between treatment and outcome.

Power analyses

Consistent with the FOA, this study will adequately power tests of target engagement (Aim 1) for traditional significance, while the "Go" signal for therapeutic impact (Aim 2) is based on effect size ($d=0.5$). To detect target engagement with $d=0.5$, 80% power, $\alpha=0.05$, test-retest correlation =0.8, and a linear treatment effect, $n=27$ randomized participants are required per group. This is a very conservative estimate of d for target engagement, since empirically, d for target engagement with 5 mg amphetamine was 0.85 (Fig. 3A). A future Confirmatory Efficacy trial will be powered to apply more robust approaches to Aim 2, e.g. Path Analysis¹⁰⁸ to study moderating effects of APS AMPH sensitivity and biomarkers on both indirect (moderated-mediation) and direct paths between treatment and outcome.

Project Modification: Statistical Analysis Plan

The original study design included separate, parallel assessments of amphetamine (AMPH) (vs. placebo (PBO)) and memantine (MEM) (vs. PBO) effects on TCT-associated clinical, neurocognitive and functional gains. However, these designs pre-dated the pandemic, and between the date that they were proposed (10/2019) and the project start date (8/2020), our institution implemented a pandemic-related shut-down of clinical research activities. Even with the gradual resumption of research activities, recruitment lagged significantly behind target levels. As a result, we made several pragmatic adjustments to the original study designs:

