1) Two separate but parallel protocols were approved by the UCSD IRB (protocols #191811, #201502) and posted on ClinicalTrials.gov. Due to the low recruitment numbers, the two parallel studies were combined and placebo groups were pooled, to yield a 3-group design 2) subject randomization changed from 1:1 to a 2:1 active : placebo ratio; and 3) adjustments were made to the planned statistical analyses, appropriate to the reduced sample size.

Based on known benefits of TCT in psychosis patients, no “placebo TCT” condition (e.g., video game) was included, for ethical and pragmatic reasons. Since all subjects received TCT, clinical gains over time in all groups might reflect, to some degree, the benefits of TCT. Pharmacologic augmentation by AMPH would only be evident if/when benefits in “TCT+active drug” groups exceeded those in “TCT+PBO” groups.

The primary goal of this study was to assess the clinical, neurocognitive and functional gains associated with the addition of AMPH to a full course of TCT. In total, there were 3 primary outcome measures and 5 secondary outcome measures. The primary clinical outcome measure was the Positive and Negative Symptom Scale (PANSS) total score; positive and negative subscale scores were secondary outcomes. Because they were highly correlated with total scores ($r=0.92$ at T_1), PANSS general scores are reported but are not outcomes. The primary neurocognitive outcome was the MCCB Composite Score. The primary functional outcome was the World Health Organization Disability Assessment Schedule (WHODAS 2.0, 12-item). Secondary clinical outcome measures also included the Patient Health Questionnaire (PHQ-9), the Young Mania Rating Scale (YMRS) and the Psychotic Symptoms Rating Scale (PSYRATS) hallucinations subscale.

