Clinical, neurocognitive and functional outcome scores were treated as continuous variables and analyzed in three ways. First, they were submitted to linear mixed-effects (LME) models⁵⁹ for both between-group (interaction model: TCT+AMPH vs. TCT+PBO) and within-group (time model: baseline vs. P30, all groups) analyses. LME analyses included data from all randomized subjects (including those who did not complete 30 AT sessions) and modeled random intercepts to account for within-subject dependencies. Second, because sample sizes fell well below target levels, to test the hypothesis that active drugs would augment the impact of a 30-session course of TCT, the effect size (Cohen's d) of the change from baseline to P30 (“difference score”) was calculated for both between-group (TCT+AMPH vs. AT+PBO) and within-group (baseline vs. P30, all groups) comparisons. Between-group effect sizes were calculated as:

$$d = [(drug score T_1 - drug score P30) - (PBO score T_1 - PBO score P30)] / SD_{wav}$$

where SD_{wav} is the weighted average standard deviation. Within-group effect sizes were calculated as:

$$d = (score at T_1 - score at P30) / SD_{av}$$

where SD_{av} is the average of the standard deviations of the T_1 and P30 measures^{60,61}.

Third, to disentangle the salutary contributions of TCT alone vs. TCT+active drug to within-subject effect sizes, a “threshold” for positive active drug effects was set at “*d=0.4 above PBO values*”:

$$d(\text{active drug}) \geq d(\text{PBO}) + 0.4.$$

Because clinical gains from TCT+PBO were expected to be approximately $d=0.4$, this added threshold of “ $d=0.4$ above PBO” for drug-enhanced TCT meant that an estimated combined large effect size (at least $d=0.8$) would be required for a drug effect to be viewed as meaningful. Outcomes using thresholds from $d=0.2$ to $d=0.6$ were reported.

The use of effect size comparisons in addition to p-values is common in clinical trials research as a way to measure effects independent of sample size. It is particularly useful when, as in the current study, sample sizes fall below targets identified based on traditional power analyses. Effect size “thresholds” have been used by others to argue that TCT neurocognitive benefits exceed levels produced via PBO or practice effects (generally $d \approx 0.18$).

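### The modified SAP counts three primary outcomes without APS learning and defines effect sizes only to P30, so on its own it cannot apply the trial's Go rule or address durability

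*SAP*

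**What the plan says.** Protocol section 4.3, Outcome Measures, lists four primary outcomes. The first is APS learning: "More learning (greater gain in processing speed) with amphetamine vs. placebo confirms target engagement, which is the primary outcome of Aim 1". The others are PANSS total, the MCCB composite and WHODAS, each measured at baseline, after sessions 10, 20 and 30, and 12 weeks after training ends.

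The protocol's text on outcomes and Go decisions makes the first requirement for a Go "confirmation of target engagement (APS learning, AMPH>PBO", at p<0.05. Fig. 8 has the same structure: criterion #1 is target engagement, and at least one of #2 (greater), #3 (faster) or #4 (more durable) must also be met. The Fig. 7 legend says that the post-treatment "tests assess both immediate biomarker changes and 12-week durability of outcome gains". The protocol's Aim 2 analysis text and the SAP's Go/No-Go section both define analyses for faster and for more durable gains. The SAP's list of primary efficacy endpoints still has APS learning under Aim 1.

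The Project Modification at the end of the SAP reads differently. It restates the purpose: "The primary goal of this study was to assess the clinical, neurocognitive and functional gains associated with the addition of AMPH to a full course". It gives the totals as three primary and five secondary outcomes and names all eight; APS learning is not among them. Scores are analysed in three ways. The effect size is that "of the change from baseline to P30", for both between-group and within-group comparisons, and the 0.4 threshold is built on the within-group version. The within-group mixed model is baseline against P30. The between-group interaction model names no time points. The section does not mention APS learning, target engagement, the Go rule, sessions 10 and 20, the 12-week visit, or the regression of clinical gain on target engagement. The only reason it gives is that the analyses were adjusted to suit the smaller sample.

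**The concern.** The trial was set up as a chain: show that the drug improves learning in a one-hour test, then see whether that carries through to greater, quicker or longer-lasting gains. The modified plan specifies only one link, the size of the gain at P30. A reader with that section alone could not tell whether the first Go condition was met, or whether any benefit came early or lasted. The protocol, under its limitation on ceiling effects, says that onset and durability were not assessed in the group's earlier studies and matter clinically.

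The Project Modification is written in the past tense and quotes an observed correlation (r=0.92 at T1), so at least some data existed when it was written. A change in the list of primary outcomes at that stage needs an explicit statement and a reason.

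**Working it through.** **Step 1. The plan's own sample size.** Inputs: "Hypothesis tests are 2-sided" with alpha 0.05 (SAP, General Statistical Approach); "To detect target engagement with $d=0.5$, 80% power" and "test-retest correlation =0.8, and a linear treatment effect" (SAP, Power analyses).

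- SD of the change score, in units of the raw SD: √(2(1−0.8)) = √0.4 = 0.632.
- Normal approximation: n = 2(1.960+0.842)² × 0.4 / 0.5² = 25.1, so 26 per group.
- With the noncentral t: 27 per group, power 81.3%.

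This reproduces the stated 27. The calculation is for APS learning and is the only sample-size calculation in the documents. The measure absent from the modified list is therefore the one the trial was sized for. This gives context; it does not itself prove a gap.

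**Step 2. The two plans side by side.**

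| Question | Protocol and earlier SAP text | Project Modification |
|---|---|---|
| Target engagement (APS learning) | Primary; Go criterion #1, p<0.05 | Not mentioned |
| Greater gains, 3 outcomes | Go criterion #2 | Between- and within-group d to P30; threshold; mixed models |
| Faster gains, 3 outcomes | Go criterion #3, from the drug × session interaction | Interaction model with no time points or session contrast named |
| More durable gains, 3 outcomes | Go criterion #4, week 12 | Not mentioned |

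**Step 3. Count.** The protocol asks 1 + 3 × 3 = 10 primary questions. The modified plan defines an effect size for 3 (greater, at P30). For 4 (APS learning, and week 12 for three outcomes) it mentions neither the measure nor the visit. The other 3 (faster) are unclear, because the interaction model may use session 10 and 20 data. Effect sizes are defined at 1 of 4 scheduled post-baseline visits.

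**Step 4. The Go rule.** Fig. 8 requires #1 and at least one of #2, #3 and #4; the accompanying text adds that adverse effects must not be significantly greater than on placebo. If #1 is not evaluated, a favourable P30 result cannot give a Go. If P30 falls short, #3 or #4 could still be met, so P30 alone does not settle a No-Go either.

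**Step 5. Does the smaller sample explain the omission?** Achieved arm sizes are not given. The allocation is also unclear: 2:1 in each of two protocols with pooled placebo makes AMPH : memantine : placebo 2 : 2 : (1+1), so AMPH against placebo could be near 1:1 and not 2:1. Under assumed sizes, with the change score, d=0.5 and r=0.8, t-based power for APS learning would be:

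| AMPH vs PBO (assumed) | Power |
|---|---|
| 27 vs 27 | 81% |
| 36 vs 18 | 77% |
| 18 vs 18 | 64% |
| 24 vs 12 | 58% |
| 18 vs 9 | 46% |
| 10 vs 10 | 39% |

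A significance test weakens as numbers fall, but an estimate with an interval remains available. The Project Modification itself argues for effect sizes when recruitment falls short, and that argument covers APS learning and week 12 equally. APS learning should also lose the fewest patients: Tests 1 and 2 come before the 30 sessions, over which the protocol expected numbers to fall from 54 to 36.

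**The case against.** The strongest reply is that nothing has been removed. The Project Modification is appended to an SAP that still lists APS learning as the Aim 1 endpoint, bases Go/No-Go on it, and defines the faster and durable analyses. The sentence counting three primaries closely follows one confined to clinical, neurocognitive and functional gains, and matches the protocol's choice of one primary measure in each of those domains. This stands in part. A reader might infer that APS learning was deleted; the documents do not say so. They do give a total that conflicts with the earlier list, and they do not say which governs.

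Second, session 10 and 20 data may enter the between-group interaction model, which includes patients who stopped early. This stands. The faster part is weaker than the APS and week-12 parts, and a flat claim that six of the nine Aim 2 questions go unestimated would be too strong.

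Third, the protocol itself warns that a small sample limits the number of outcomes and that rate and durability triple the primary analyses. That is a fair reason to concentrate testing on P30. It is not a reason to leave the other questions without an estimate or an explanation.

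Fourth, a reader might infer that a null P30 result could not count as a valid negative without target engagement. The protocol offers that case only as an example and also discusses what can be learned if engagement is not confirmed, so the inference fails.

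**Conclusion.** The concern holds as a conflict between the modified plan and the rest of the documents. The Project Modification counts three primaries where the protocol has four. It defines no estimate for APS learning, none for week 12, and no session-specific contrast. Followed alone, it cannot apply the stated Go rule or address durability. The APS and week-12 gaps are firm on the text; the session 10 and 20 gap is one of specification.

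This rests on reading the count of primaries as complete and on taking the outcome schedule as unchanged. The documents do not confirm that every scheduled visit was held under the modified conduct. A reader might also suspect selective reporting, since the section was written with some data in hand. The documents show no motive, and that inference should not be drawn; the remedy is an explicit statement of what changed and why. This should be corrected before results are interpreted against the Go criteria.

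**What to change.** In the Project Modification, state for APS learning, sessions 10 and 20, week 12 and the regression on target engagement whether each is kept, moved or dropped, and why. Then:

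1. Keep APS learning as the Aim 1 primary. Report the between-arm contrast of the change from Test 1 to Test 2, in all randomised patients with available data, with d and 95% CI. State that this replaces the protocol's Aim 1 rule, which accepts either a within- or a between-subject contrast, because the within-arm change includes practice effects.
2. For PANSS total, MCCB composite and WHODAS, report between-group d with 95% CI at week 12 and, descriptively, at sessions 10 and 20, where collected.
3. State whether Go/No-Go is still made from Fig. 8. Criterion #3 needs an interaction at p<0.05, so descriptive estimates cannot satisfy it. If criterion #1 or #3 is not tested, say that no Go decision is made on it.

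The cost is SAP wording and a few estimates from scheduled data. Intervals will be wide: even at the planned 18 completers per arm, the approximate half-width for a between-group d is 1.96 × √(1/18+1/18) = 0.65, and the achieved numbers fell below target. There is also one more primary result to report, which may be unfavourable.

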NCT4414930: Pharmacologic augmentation of targeted cognitive training in schizophrenia
Statistical Analysis Plan

October 11, 2019

Statistical Design & Power

Design (see “Research Strategy”, Figure 7): Screened, eligible patients complete clinical, neurocognitive and functional measures and candidate biomarkers. In Test 1, all subjects are tested in Sound Sweeps after PBO, and then assigned to TCT+PBO vs. TCT+AMPH arms (n=27/arm) using stratified random sampling (over sex, age and high/low Test 1 (baseline) APS learning) blind to arm identity, similar to¹⁰⁷. Stratifying for baseline APS learning should increase the sensitivity of the primary target engagement metric. An example of a table for arm assignment is seen here:

Gender	Baseline	Age	Group								
Male	High	< 39	PBO	PBO	AMPH	AMPH	AMPH	AMPH	PBO	PBO	PBO
	High	≥ 39	PBO	AMPH	PBO	AMPH	AMPH	PBO	AMPH	PBO	PBO
	Low	< 39	AMPH	AMPH	PBO	PBO	PBO	PBO	AMPH	AMPH	AMPH
	Low	≥ 39	AMPH	PBO	AMPH	PBO	PBO	AMPH	PBO	AMPH	AMPH
Female	High	< 39	PBO	PBO	AMPH	AMPH	AMPH	AMPH	PBO	PBO	PBO
	High	≥ 39	PBO	AMPH	PBO	AMPH	AMPH	PBO	AMPH	PBO	PBO
	Low	< 39	AMPH	PBO	AMPH	PBO	PBO	AMPH	PBO	AMPH	AMPH
	Low	≥ 39	AMPH	AMPH	PBO	PBO	PBO	PBO	AMPH	AMPH	AMPH

Example of table for stratified random sampling, by gender, baseline APS learning (post-PBO) and age (based on approximate mean age (39 yo) of last 100 SZ patients tested in our program)

Test 2 follows approximately 5-7 days later. Tests 1 and 2 are used to assess target engagement (Aim 1: AMPH-enhanced APS learning) and AMPH effects on auditory discrimination. Our design allows for 20% attrition from enrollment (n=69) to completion of target engagement testing (n=54).

For Aim 2, TCT is scheduled 3 d/week and continues until a subject completes 30-h (approximately 10-12 weeks). 60 min prior to each TCT session, patients take either PBO or 5 mg AMPH, as per arm assignment. Patients and staff are blind to study arm; staff are blind to patients’ baseline or post-intervention assessments. Outcome measures are assessed after sessions 10, 20 and 30, and 12 weeks post-TCT. See “Research Strategy” for details.

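### The SAP's undated modification adds a data-era rule for a meaningful drug effect (0.4 above placebo, no interval) and does not say whether the pre-specified d ≥ 0.5 Go rule still governs

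*SAP*

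**What the plan says.** The SAP's title block is dated "October 11, 2019", and no other document date appears. Its Power analyses section says that the Go "signal for therapeutic impact (Aim 2) is based on effect size", with d = 0.5. The protocol agrees. Its Go-decision text asks for d of at least 0.5 for AMPH over PBO, and its Aim 2 analysis takes that d from the drug main effect or the drug-by-session interaction in a linear mixed model.

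The SAP then adds a section headed Project Modification, which has no date or version. It reports in the past tense that "recruitment lagged significantly behind target levels", that placebo groups were pooled with those of a parallel memantine study, and that allocation moved to 2:1 active to placebo. It cites a T_1 correlation of 0.92 when explaining that "PANSS general scores are reported but are not outcomes".

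The section describes three analyses:

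1. Mixed models in all randomized subjects, at alpha 0.05.
2. Effect sizes for the change from T_1 to P30, introduced with "Second, because sample sizes fell well below target levels".
3. A threshold on within-group effect sizes, d(active) ≥ d(PBO) + 0.4. With an expected placebo-arm gain of about 0.4, it says that a combined d of at least 0.8 is needed "for a drug effect to be viewed as meaningful". Results at thresholds from 0.2 to 0.6 are said to have been reported.

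The effect sizes use completers only. The section defends effect sizes, alongside p-values, "as a way to measure effects independent of sample size". It plans no interval for any of them and does not mention the 0.5 Go rule.

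**The concern.** A rule for calling an effect meaningful carries weight if it was fixed before the data could influence it and if its error rate is known. Neither is shown here. The modification postdates knowledge of enrolment and of T_1 scores, but it does not say when it was written, what else had been seen, or whether its authors were blinded. It introduces a different quantity (the difference of two within-group d values) and a different margin, and shows the result at a range of thresholds. It leaves open how this relates to the Go rule in the same document.

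The point estimate is also used where it is least reliable. The expected size of d hardly depends on sample size, but its precision does. A small completer set can produce a difference of 0.4 by chance, and without an interval the reader cannot tell. At stake is whether a finding that amphetamine meaningfully augments training, and hence a decision to proceed to a confirmatory trial, rests on noise.

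**Working it through.** **Inputs from the documents.** Planned completers: 18 per arm (protocol, Recruitment and Retention Plan). Expected placebo-arm gain: d ≈ 0.4 (SAP, Project Modification). Within-group d: mean T_1 minus mean P30, divided by the average of the two raw-score SDs (same section). The only correlation given is a test-retest value of 0.8, used for Aim 1 (SAP, Power analyses).

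**Assumptions.** Achieved completer numbers and the T_1–P30 correlation r for PANSS, MCCB and WHODAS are not given. I use r from 0.8 to 0.5 and AMPH/PBO completers of 18/18, 20/10 and 10/10. Equal arms remain plausible after the change: two equal-sized studies at 2:1 with pooled placebo give 2 : 2 : (1+1).

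**1. The plan's own figure.** With r = 0.8, the SD of change is √(2(1−0.8)) = 0.632. Then n = 2(1.96+0.842)² × 0.632² / 0.5² ≈ 25.1, so 26 per group by the normal approximation. With the t distribution, 26 gives 79.8% power and 27 gives 81.4%. The stated 27 is reproduced. It concerns Aim 1 and does not support the 0.4 margin.

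**2. Are 0.4 and 0.5 on one scale?** A difference of 0.4 in raw-score SDs equals 0.4/√(2(1−r)) change-score SDs: 0.63 at r = 0.8, 0.48 at r = 0.65 and 0.40 at r = 0.5. The documents do not name the SD behind the mixed-model d of Aim 2. Chance of passing for one outcome at 18/18 with no drug effect (simulation, 40,000 runs):

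| Rule | r = 0.8 | r = 0.65 | r = 0.5 |
|---|---|---|---|
| New: d(active) − d(PBO) ≥ 0.4 | 5.1% | 9.2% | 13.2% |
| d ≥ 0.5 on change-score SD | 7.3% | 7.1% | 7.2% |
| d ≥ 0.5 on raw-score SD | 1.2% | 4.1% | 7.3% |

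The new rule can be stricter or looser than the Go rule, depending on a scale the plan does not state.

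**3. Precision.** Approximate SE of d(active) − d(PBO) = √(2(1−r)(1/n_A + 1/n_P)). At r = 0.7:

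- 18/18: √(0.6 × 0.111) = 0.26, so an observed 0.4 has a 95% interval of about −0.1 to 0.9.
- 20/10: √(0.6 × 0.15) = 0.30, giving about −0.2 to 1.0.

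This formula ignores the sampling error of the SDs, so the true intervals are somewhat wider.

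**4. Chance of passing 0.4 with no drug effect** (both arms gain 0.4):

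| Completers AMPH/PBO | One outcome, r = 0.8 to 0.5 | Any of three independent primaries, 1 − (1−p)³ |
|---|---|---|
| 18/18 | 5.1% to 13.2% | about 15% to 35% |
| 20/10 | 6.8% to 16.1% | about 19% to 41% |
| 10/10 | about 11% to 20% | about 30% to 49% |

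Correlated outcomes reduce the last column: with inter-outcome correlation 0.3, the 18/18 range is about 13% to 30%. For comparison, a two-sided test at 0.05 gives 2.5% per outcome in the favourable direction.

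**5. The threshold range.** At 20/10, the single-outcome rate runs from 22.6–31.0% at threshold 0.2 to 1.4–6.9% at 0.6. If the true added gain is exactly 0.4, the rule passes about half the time at any sample size.

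**The case against.** The best defence is that this is an openly labelled modification to a pilot. It describes the pandemic, the 2020 start and the shortfall, so an attentive reader would not date it to 2019. Mixed-model tests at alpha 0.05 in all randomized subjects remain. The Go rule was itself a point-estimate rule, explained by the funder's call for pilot studies. The phrase about sample size contrasts d with p-values. The 0.2–0.6 range is centred on 0.4 and can be read as a sensitivity display. All of this stands and limits the point, but it does not supply an interval, an error rate or a statement of which rule governs.

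A reader might also infer more than the documents support:

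- *That the bar was lowered, or that 0.4 replaced 0.5.* The text does not mention 0.5, and the comparison of scales leaves the direction open.
- *That PANSS general was dropped as an outcome after its correlation was seen.* The protocol never named it as one. The correlation shows only that T_1 data had been examined, and T_1 precedes randomization with every subject on placebo, so it says nothing about treatment effect.
- *That the threshold was chosen unblinded.* The past tense about reported results is suggestive, but nothing states this.
- *That crossing 0.2 counts as success.* The stated threshold is 0.4.

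**Conclusion.** The point holds in this form. An undated modification, written after enrolment and T_1 data were known, adds a criterion for a meaningful drug effect that rests on a completers-only point estimate without an interval, and it is silent on the pre-specified Go rule. Followed as written, it can label a chance difference as meaningful: about 5–13% per outcome at 18/18, 7–16% at 20/10 and 11–20% at 10/10, and more often if any of three primaries suffices. These figures rest on assumed completer numbers, correlations of 0.8 to 0.5, normal scores and an equal gain of 0.4 in both arms. What is new relative to the Go rule is the timing, the metric and the multiple thresholds. A lowered bar and an unblinded choice are not shown. The correction is needed before any statement that a drug effect was meaningful is relied on.

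**What to change.** 1. Report a 95% interval, analytic or bootstrap, with every between-arm d and every d(active) − d(PBO).
2. State that the between-arm d ≥ 0.5 remains the Go threshold for Aim 2, and name the SD that standardizes it.
3. Label the 0.4-above-placebo rule and the 0.2–0.6 range post hoc and exploratory.
4. Date and version the modification. State which data had been seen when it was written and whether the authors were blinded to arm.
5. Replace the claim of independence from sample size with a statement that the expected size of d is roughly independent of n, while its precision is not.

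The cost is SAP wording and a short calculation on data already held, with no new data. The downside for the sponsor is that a result at the 0.4 threshold becomes a less favourable, exploratory statement.
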